6.1 Statistical considerations

All calculations will be performed on the basis of intention to treat. 2 sided tests will be performed. Level of type 1 error is 5%.

6.2 Sample size calculation:

Observed local failure free survival rate after 9 months after initiation of radiation was 70% among 300 patients treated in Odense for NSCLC stage IIB-IIIB. The study will be designed to find local recurrence free survival of 80% at 9 months after initiation of radiation equivalent to about 6-7 months after finishing radiotherapy. A rate of 80% would be clinically interesting, and should be included in the confidence interval of the phase II trial at a power of 90%. This requires 57 patients to be included in the phase II trial.

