1.1 Concurrent chemo-radiotherapy

Lung cancer is the major cause of cancer-related death in Europe and North America. About 75% to 80% of lung cancer is non-small-cell cancer (NSCLC) with approximately 40% of patients presenting with locally advanced disease. In patients with no malignant pleural effusions, the treatment options have been irradiation up to 60-70 Gy against the primary lung tumor and lymph nodes in mediastinum resulting in a median survival of 6 to 11 months and 5 years survival of 5%. The treatment have until recently consisted of irradiation of the tumor bed and areas around with high risk of relapse. The treatment has now being optimized by giving chemotherapy either before irradiation or concomitant with radiation or both. The irradiation technique have been improved by introduction of 3D-CT-scan based planning technique, and the prognosis have been somewhat improved. Data from Odense shows a 5 year survival rate of 16% at 5 years (1). The treatment of choice for locally advanced NSCLC is radiotherapy combined with chemotherapy since trials using inductions chemotherapy and/or concomitant chemotherapy have demonstrated increased median survivals to 13-15 months with a 5 years survival of 10-20%. The rationale for using of inductions chemotherapy has been to reduce the treatment volume by reducing the tumor burden and to eradicate micro-metastases.

A significant problem in the treatment of local advanced NSCLC is a high rate of local failure of up to 45% without distant metastases after irradiation. In 200 patients with NSCLC stage III treated in Odense the 1 year survival was 61%. 112 of these had received a platinum based induction chemotherapy regimen, and 3 had concomitant therapy with Taxotere. The local failure free survival was 70% 9 months after start of irradiation and 43 % after one year (unpublished data).

The poor local control is partly due to the tumors content of radio-resistant cells in hypoxic areas of the tumor. The radio-resistance is in part due to an up-regulation of the epidermal growth factor receptor (EGFR). The radio-resistance of the tumor cells can be overruled at least from a theoretical point of view by using concomitant treatment with drugs, which either can bring the tumor cells in phases of the cell cyclus in which they are more sensitive to irradiation (G₂- and M-phase) or specifically kill the hypoxic cells.

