3.1 Study design

The treatment plan is consisting of radiation; 3-D conformal radiotherapy given together with Tarceva 150 mg/day. Induction chemotherapy may be used. No concurrent chemotherapy may be used.

Figur 1: Time line in the study

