5.3 Monitoring during therapy

The patient may receive induction chemotherapy before inclusion in the study, and is as such not part of the study. The patients cannot be included in the study before a plan has been worked out showing that curatively intended radiation is possible, and informed consent has been obtained (Fig. 1).

	Screening/ Baseline	Treatment Period Timing	Day 30-45 after stop of treatment
Informed Consent	x	-	-
Demographics	x	-	-
Medical history	x	-	-
Physical examination	x	Weekly	x
Body weight	x	Weekly	x
Laboratory ¹	x	Weekly	x
ECG	x	-	x
Lung functions test ²	x	-	x
Lung CO diffusion test	x	-	-
CT scan thorax and upper abdomen	x	-	x
Tumor measurements	x	-	x
PET-CT ³	x	-	-
CT scan brain ⁴	x ⁴	-	-
Performance Status (PS)	x	Weekly	x
Side effects ⁵	-	Recorded weekly	x
Study drug compliance ⁶	-	x	x
Smoking status	x	Recorded Weekly	x

¹ Hematology: Hemoglobin, WBC, granulocytes and platelet count, INR (Only for patients receiving warfarin or coumarin-derivative). Biochemistry: Alkaline phosphatase, Serum bilirubin, Serum creatinine, ALAT (SGPT), LDH. Only laboratory abnormalities linked to unexpected clinical symptoms will be documented in the CRF.

² FEV₁/FVC test. If neoadjuvant chemotherapy, the test must be performed after cessation of chemotherapy.

³ CT scans, PET CT scans per institutional standards, EBUS or mediastinoscopy may be accepted as mediastinal evaluation if PET-CT is not available

⁴ If no PET-CT available

⁵ Side effects to be recorded according to CTC version 3.0

⁶ Pharmacy log

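### The single 70% Odense benchmark in section 6.2 is not matched to the trial's induction-chemotherapy mix, so a difference in mix could mimic or mask an erlotinib effect of unknown size

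*Protocol*

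**What the plan says.** Protocol section 6.2 takes its reference rate from a historical series: "Observed local failure free survival rate after 9 months after initiation of radiation was 70% among 300 patients treated in Odense", stage IIB-IIIB. The rate of interest is a chosen target: "A rate of 80% would be clinically interesting, and should be included in the confidence interval of the phase II trial at a power of"; the figure given there is 90%. The size follows: "This requires 57 patients to be included in the phase II trial". Neither rate depends on prior treatment, and there is no control arm.

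Section 1.1 describes an Odense series of 200 stage III patients, also with 70% local failure free survival at 9 months. On their treatment it says: "112 of these had received a platinum based induction chemotherapy regimen, and 3 had concomitant therapy with Taxotere". The protocol does not say whether these 200 are among the 300 of section 6.2, and it gives no induction share for the 300.

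For the trial itself, section 3.1 says: "Induction chemotherapy may be used. No concurrent chemotherapy may be used". Section 5.3 adds: "The patient may receive induction chemotherapy before inclusion in the study, and is as such not part of the study". Nothing in the protocol sets, limits or adjusts for the share of patients who come in after induction.

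**The concern.** In a one-arm trial the historical rate does the work of the control group. The 70% is an average over patients with and without induction. If the trial's mix differs and induction status is related to local failure by 9 months, then 70% is not the rate to expect without erlotinib.

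The protocol itself presents chemotherapy as improving outcome. Section 1.1 gives median survival of 6-11 months for irradiation and 13-15 months in trials of induction and/or concomitant chemotherapy. The same section also notes that some patients are unfit for chemotherapy or refuse it, so the enrolled mix could differ from that of Odense.

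The error can go either way. If induction goes with better local control, a trial with more induction than Odense could come in above 70% with no drug effect. A trial with less induction could show about 70% despite a real gain. The one fixed benchmark cannot tell these cases apart.

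**Working it through.** **1. The plan's own figure.** A normal-approximation confidence interval of half-width 10 points around 70% needs n = z² p(1-p)/h². With z = 1.645 (two-sided 90% interval), p = 0.70 and h = 0.10, n = 2.706 × 0.21 / 0.01 = 56.8, so 57. The stated size is therefore reproduced as an interval around the single 70%, with no term for patient mix. (It is not the size of a test of 70% against 80% with 90% power at two-sided 5%, which needs about 199. That is a separate matter.)

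**2. The induction share.**
- 200-patient series (section 1.1): 112/200 = 56%, exact 95% CI 49% to 63%.
- 300-patient benchmark (section 6.2): not stated. If the 200 were all among the 300, the share would lie between 112/300 = 37% and (112 + 100)/300 = 71%.

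**3. How mix moves the no-effect rate.** Let s be the trial's induction share and D the 9-month rate with induction minus the rate without. Anchoring 70% at a 56% share, as observed in the 200-patient series, gives:

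no-effect rate = 0.70 + (s - 0.56) × D

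The protocol does not give D, so these values are assumptions, including the positive sign:

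| D (points) | s = 0% | s = 40% | s = 80% | s = 100% |
|---|---|---|---|---|
| 5 | 67.2% | 69.2% | 71.2% | 72.2% |
| 10 | 64.4% | 68.4% | 72.4% | 74.4% |
| 15 | 61.6% | 67.6% | 73.6% | 76.6% |

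**4. What a 5-point shift would need.** D = 0.05 / |s - 0.56|:
- no induction at all: 0.05/0.56 = 8.9 points
- induction for all: 0.05/0.44 = 11.4 points
- 80% induction: 0.05/0.24 = 20.8 points
- 40% induction: 0.05/0.16 = 31.2 points

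A shift of that size therefore needs an extreme mix or a large subgroup difference.

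**5. What a shift would do at n = 57 (exact binomial, illustrative).** Section 6.2 states no success rule beyond 80% lying in the confidence interval, so two readings are shown. The upper limit of the exact 95% CI reaches 80% from 39/57. The lower limit exceeds 70% from 47/57.

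| True rate without drug effect | CI reaches 80% | CI lies above 70% |
|---|---|---|
| 65% | 35% | 0.3% |
| 70% | 66% | 2.4% |
| 75% | 90% | 12.4% |

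The reading is sensitive to a shift of 5 points, if one occurs.

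**6. Precision of a matched benchmark.** On the 200-patient counts, 112 had induction and 88 did not. About 85 of the latter remain if the 3 docetaxel patients are removed and had no induction. At a rate of 70%, the 95% margins are:
- pooled, n = 200: 1.96 × √(0.21/200) = 6.4 points
- induction, n = 112: 1.96 × √(0.21/112) = 8.5 points
- no induction, n = 85: 1.96 × √(0.21/85) = 9.7 points
- weighted to s = 20%: 1.96 × √(0.2² × 0.21/112 + 0.8² × 0.21/85) = 8.0 points
- weighted to s = 80%: 1.96 × √(0.8² × 0.21/112 + 0.2² × 0.21/85) = 7.1 points
- the trial itself, n = 57: 1.96 × √(0.21/57) = 11.9 points

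**The case against.** The strongest objection is that no bias has been shown. The described Odense series was itself a mixture with almost no concurrent chemotherapy (3 of 200), so an optional-induction trial resembles it. Eligibility in section 5.1 does not require unfitness for chemotherapy, and sections 4 and 4.1 plan for patients who have had induction. Nothing points to an extreme mix. This stands, and it is why the size must be left open.

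A reader might infer that mix alone moves the benchmark by 5 points or more. One route is to turn the survival medians of section 1.1 into 9-month rates. The protocol does not support that. Those medians are for overall survival, not local failure. The higher ones cover induction and/or concomitant chemotherapy, and the text also credits better planning technique with part of the improved prognosis. The proxy also misses the protocol's own data: mid-range medians of 8.5 and 14 months with exponential survival, mixed 44:56, predict 0.44 × 37.6% + 0.56 × 55.2% = 47% alive at one year, against 61% observed in the 200-patient series.

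A second objection is that splitting the benchmark costs precision, with subgroup margins of about 8.5 to 10 points. This stands in part. At induction shares of 20-80% the weighted margin is only about 6.4 to 8 points, still below the trial's own 12.

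Third, reporting by induction status can be left to the analysis plan, and induction status may already be captured under medical history. Accepted: no missing data item is alleged. The point concerns the benchmark, which section 6.2 itself fixes.

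**Conclusion.** The point holds in a limited form. Section 6.2 ties a one-arm trial to one external rate whose induction mix is not stated and is not matched to the trial, while induction is optional. A difference in mix therefore cannot be separated from an erlotinib effect.

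Size and direction cannot be determined from the protocol. Over all possible mixes, assumed subgroup differences of 5, 10 and 15 points give no-effect rates of 67-72%, 64-74% and 62-77%. At shares of 40-80% the shift stays below 4 points for each of these. The figures rest on the 56% share of the 200-patient series and on an assumed difference.

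Three further readings go too far. The 56% is an observed share in stage III patients and cannot be assigned to the 300 patients behind the benchmark. The 80% is a chosen target, not an Odense result. And the risk is not only a false positive: with fewer induction patients than in Odense, and if induction helps local control, a real effect would be hidden. The point is a cheap improvement to how the result is read and does not show that the benchmark is wrong.

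**What to change.** In section 6.2:
1. State the induction share of the Odense series used for the benchmark, and tabulate its 9-month local failure free survival with and without induction, leaving out patients with concomitant chemotherapy.
2. State in advance that the trial's 9-month rate and 95% CI will also be read against the Odense rate weighted by the induction share actually enrolled: s × (rate with induction) + (1 - s) × (rate without).
3. Report the primary endpoint by induction status beside the matching Odense rate.

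Keep the 70%/80% pair as the sizing assumption. Eligibility and treatment are not affected.

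The cost is one re-tabulation of data that the sponsor already used and a short paragraph. The downsides are modest. The weighted benchmark is somewhat less precise than the pooled one (95% margin about 6.4 points near the Odense mix, up to about 10 at an extreme mix, on the 200-patient counts). It corrects for induction only, not for stage or performance status. It becomes final only when the enrolled mix is known.

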1.3 Tarceva

Tarceva (Erlotinib hydrochloride) is a quinazolinamide that inhibits the intracellular tyrosin kinase domain of the EGFR. It is formulated as immediate release tablets. Bioavailability of Erlotinib following a 150 mg oral dose is about 60% (and almost 100% if taken together with food) and peak plasma levels occur 4 hours after dosing. The median half-life is 36 hours, and the time to reach steady-state plasma concentration is 7-8 days (12). Smokers have a 24% higher rate of Erlotinib clearance. Erlotinib is metabolized by the liver cytochrome P450 system primarily by CYP3A4 which may be a cause of interaction with other drugs.

2. Objectives of the study

The trial is a phase II study of daily Tarceva combined with definitive radiotherapy in inoperable locally advanced non small cell lung cancer (stage IIB-IIIB).

The objective of the phase II trial is to examine Tarceva concomitant with curatively intended irradiation 66 Gy (2 Gy x 33 F, 5 F per week):

Primary endpoint

- Local failure free survival at 9 months after start of radiotherapy evaluated at CT scan.

[figure not shown]
Secondary endpoints

- Toxicity
- Local tumor control by CT-scan
- Overall response rate (CR + PR).
- Local tumor control at 9 months evaluated by PET-CT
- Overall survival
- Disease free survival
- Late toxicity

3. Study design and dosing regimen

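### The one efficacy criterion in section 6.2, that the confidence interval includes 80%, separates 80% from the historical 70% poorly, and its 90% power is in effect a confidence level

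*Protocol*

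**What the plan says.** The primary endpoint in section 2 is "Local failure free survival at 9 months after start of radiotherapy evaluated at CT scan".

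Section 6.1 fixes the error rate for the whole plan: "2 sided tests will be performed. Level of type 1 error is 5"%.

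Section 6.2 starts from history: "Observed local failure free survival rate after 9 months after initiation of radiation was 70% among 300 patients". It sets the target: "The study will be designed to find local recurrence free survival of 80% at 9 months after initiation of radiation". It then gives the only efficacy criterion in the protocol, that a rate of 80% "should be included in the confidence interval of the phase II trial at a power of 90"%, and concludes: "This requires 57 patients to be included in the phase II trial".

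Section 6.2 does not give the level of the confidence interval or the method for it. It does not ask that the interval exclude 70%, and it does not give the chance of meeting the criterion if the true rate is still 70%. The interim analysis in section 6.3 concerns toxicity only.

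**The concern.** An interval that contains 80% shows that the data are compatible with 80%. With 57 patients the same interval can easily contain 70% as well, so meeting the criterion is not evidence of improvement on history. A test of 70% would ask the opposite question, namely whether the lower limit lies above 70%.

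The word power is also misplaced. If the true rate is 80%, the chance that the interval contains 80% is the coverage of the interval. Coverage is set by the confidence level and hardly changes with sample size, so it cannot be what makes 57 patients necessary.

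This is an uncontrolled trial, and the criterion is the only stated basis for reading its primary result. A reader who sees 90% power beside a 5% type I error will suppose that the trial can tell 80% from 70% at those error rates. It cannot do so with 57 patients.

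**Working it through.** **Inputs.** Historical rate 70%, target 80%, n = 57 and stated power 90% (section 6.2); two-sided 5% (section 6.1). Assumptions: the endpoint is treated as a simple proportion at 9 months, all 57 patients are evaluable, and 70% is the true rate if erlotinib adds nothing. Because the interval level is not stated, both 95% (matching section 6.1) and 90% are shown.

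**Step 1: reproduce 57.** A precision formula gives it:

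n = z² × p(1 − p) / d² = 1.645² × 0.70 × 0.30 / 0.10² = 56.8, rounded up to 57.

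This is a two-sided 90% normal-approximation (Wald) interval around an observed 70% with a half-width of 10 points, so that its upper limit just reaches 80%. Check: 1.645 × √(0.21/57) = 0.0998. On this reconstruction the 90% is a confidence level.

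**Step 2: what a test of 70% against 80% would need.** One-sample normal formula, two-sided 5%, 90% power:

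n = [1.960 × √(0.70 × 0.30) + 1.2816 × √(0.80 × 0.20)]² / 0.10² = [0.898 + 0.513]² / 0.01 = 199.

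The exact binomial calculation at one-sided 2.5% gives 200. At one-sided 5% the figures are 161 (normal) and 164 (exact). None is near 57.

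**Step 3: how often the criterion is met.** For each count x from 0 to 57, compute the interval, keep the counts whose interval contains 80%, and sum the Binomial(57, p) probabilities over them.

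| Interval | Counts that meet it | True 65% | True 70% | True 75% | True 80% |
|---|---|---|---|---|---|
| 95% exact (Clopper-Pearson) | 39–51 | 34.8% | 66.3% | 89.9% | 96.9% |
| 95% Wald | 39–50 | 34.8% | 66.2% | 89.5% | 94.2% |
| 95% Wilson | 40–51 | 25.1% | 55.3% | 83.8% | 95.5% |
| 90% exact | 40–50 | 25.1% | 55.3% | 83.5% | 92.9% |
| 90% Wald | 40–49 | 25.1% | 55.2% | 82.6% | 88.0% |
| 90% Wilson | 41–50 | 16.9% | 43.8% | 75.3% | 90.4% |

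Agresti-Coull and Jeffreys intervals give the Wilson rows. At a true 60% the 95% figures are 7% to 12%.

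Two results show what this means. An observed 40/57 (70.2%, in effect the historical rate) meets the criterion with every 95% interval. With the exact interval even 39/57 (68.4%) does, at 54.8% to 80.1%.

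**Step 4: a criterion that addresses 70%.** Require the lower limit of the two-sided 95% interval to exceed 70%. With the exact or Wilson interval the first count that does so is 47/57 (82.5%; exact lower limit 70.1%). The chance of 47 or more is 2.4% at a true 70% and 39.5% at a true 80%.

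**The case against.** The strongest reply is that the sentence is a precision statement. It stands under the sample size heading, 57 follows from a precision formula, and nowhere does the protocol say that the regimen will be called successful or taken forward if 80% lies in the interval. A formal decision rule may be in a statistical analysis plan that is not shown. This limits what can be said, but it does not rescue the wording: the text claims a power of 90%, and a precision calculation has none.

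The second reply is that the 95% level is inferred. That is correct, and it matters. With a 90% Wilson-type interval the chance at a true 70% is 44%, so it cannot be said without qualification that the criterion is met more often than not when erlotinib adds nothing.

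A reader might infer more than the documents support:

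- **That the trial has a false-positive rate of 55% to 66%.** These are the chances of meeting the criterion at a true 70% with a 95% interval. They would be a false-positive rate only if meeting it led to a claim of activity, which the protocol does not say.
- **That a regimen worse than history would pass.** At a true 65% it meets the criterion 25% to 35% of the time with a 95% interval, and at 60% only 7% to 12%. Such a regimen would usually fail.
- **That the criterion cannot tell 70% from 80% at all.** It does so poorly: 55% to 66% against 94% to 97%.
- **That a smaller trial would always pass more easily.** At a true 80% coverage is roughly constant, so size makes little difference. Only when the true rate is not 80% does a smaller trial meet the criterion more often.
- **That very good results are penalised.** Read literally, 52/57 (91%) fails because its interval lies wholly above 80%. It is unlikely that anyone would apply the sentence that way.
- **That 70% is ignored.** Section 6.2 opens with it, and 57 appears to be computed from it. What is missing is any requirement to exclude it.

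**Conclusion.** The point holds in this form: the only efficacy criterion in section 6.2 discriminates poorly between the historical 70% and the target 80%, and its 90% is in effect a confidence level labelled as power. A true 70% meets the criterion 55% to 66% of the time with a 95% interval and 44% to 55% with a 90% interval. For a true 80% the corresponding figures are 94% to 97% and 88% to 93%, which is simply the coverage of the interval. The power that the section claims, if taken as a test of 70% against 80% at the level in section 6.1, belongs to a trial of about 199 to 200 patients.

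The figures rest on the three assumptions listed with the inputs. Censoring before 9 months would widen the interval and make the criterion easier to meet. The result also depends on 70% being the right no-effect rate, which is itself an estimate. The relabelling of confidence as power is inferred from the formula that returns 57, since the protocol shows no calculation. The gap between 57 and about 199 does not depend on that inference.

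**What to change.** In section 6.2:

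1. Delete the reference to 90% power.
2. Restate 57 as a precision figure: a two-sided 90% confidence interval with a half-width of about 10 points around a rate of 70%.
3. State the level and method of the interval that will be reported for the 9-month rate.
4. State that inclusion of 80% in the interval is descriptive and supports no claim of activity.

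If the sponsor wants to claim benefit over 70%, add that the lower limit of the two-sided 95% confidence interval for the 9-month rate must exceed 70%. With the exact or Wilson interval and all 57 patients evaluable, this means at least 47 patients free of local failure, with an exact one-sided type I error of 2.4%. The power of about 39% at a true 80% should be reported beside it. The method has to be named, because a Wald interval would already pass at 46/57, where the one-sided error is 4.9%. If patients are censored before 9 months, the rule should be stated for the lower limit and not as a count.

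The cost is a few sentences and no extra patients. The drawback is that the trial's ability to show benefit over 70% then appears much weaker than the present text suggests. To keep a true 90% power for that comparison would take about 199 to 200 patients.

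### Section 6.2 ties 57 patients to 90% power, but 57 follows from neither a test against the historical 70% nor the stated confidence-interval criterion

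*Protocol*

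**What the plan says.** Protocol section 6.1 sets the error rate for all analyses: "2 sided tests will be performed. Level of type 1 error is 5" per cent.

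Section 6.2 starts from a reference: "Observed local failure free survival rate after 9 months after initiation of radiation was 70% among 300 patients". It then names the target: "The study will be designed to find local recurrence free survival of 80% at 9 months". The criterion is that 80% "should be included in the confidence interval of the phase II trial at a power of 90" per cent, and the power claim leads straight to the sample size: "at a power of 90%. This requires 57 patients to be included in the phase II trial".

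The section gives no formula, no confidence level or width for the interval, and no rule for declaring 70% exceeded. Section 2 makes local failure free survival at 9 months the primary endpoint, so this is the justification for the size of the trial.

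**The concern.** Section 6 states a reference rate, a target rate, a type 1 error, the sidedness, a power and a sample size. Together these look like a complete one-sample calculation, and they do not fit one another. A difference of 10 points from 70% cannot be detected with 90% power in 57 patients at a two-sided 5% level.

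The criterion as worded is also unusual. Power is the chance of rejecting a null value when an alternative is true. Section 6.2 attaches it to an interval including the alternative, which is a different event.

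Two misreadings are at stake, in opposite directions:

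- A reader who takes the 90% as power against 70% will over-interpret a result that cannot be told apart from 70%.
- A reader who applies the criterion as worded may call the treatment interesting because the interval contains 80%, although this happens often when nothing has improved.

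**Working it through.** **Inputs.** From section 6.1: two-sided, α = 0.05. From section 6.2: p0 = 0.70, p1 = 0.80, n = 57, stated power 0.90. The endpoint is treated as a binary proportion with every patient assessable at 9 months.

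**1. Reproducing 57.** None of the standard one-sample power formulas tried for 70% against 80% at the 5% level gives it. A precision formula does:

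n = z² p(1−p) / d² = 1.645² × 0.70 × 0.30 / 0.10² = 56.8, so 57.

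This is a 90% confidence interval of half-width 10 points around 70%. It contains no power term. At 95% confidence the same width needs 1.96² × 0.21 / 0.01 = 80.7, so 81 patients.

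**2. As a test against 70%.** With X ~ Binomial(57, p):

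- P(X ≥ 46 | 0.70) = 0.049, too large for an upper tail of 0.025.
- P(X ≥ 47 | 0.70) = 0.024, so 70% is rejected upwards at 47/57 (82.5%) or more.
- Power at a true 80%: P(X ≥ 47 | 0.80) = 0.395.

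The observed rate must therefore exceed the target itself before 70% is rejected. The normal approximation with null and alternative variances gives 36%, and other one-sample variants at two-sided 5% reach at most 47%. A one-sided 5% test (46 or more) has 53%.

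Sample size for 90% power by normal approximation:

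n = [(1.96 × √0.21 + 1.2816 × √0.16) / 0.10]² = 199.

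The exact test first reaches 90% at n = 200. A one-sided 5% test needs about 160, and even a one-sided 20% test needs 81.

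With 57 patients and the rule of 47 or more, power reaches 80% at a true rate of about 85.4% and 90% at about 87.3%.

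**3. As literally worded: the interval includes 80%.** The confidence level is not stated, so both common levels are shown. Ranges cover Clopper-Pearson, Wilson and Wald intervals at n = 57.

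| True rate | 90% CI includes 80% | 95% CI includes 80% |
|---|---|---|
| 80% | 88-93% | 94-97% |
| 70% | 44-55% | 55-66% |

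The first row is the coverage of the interval, which is set by its confidence level. For a Clopper-Pearson 90% interval it is 95.6% at n = 20, 92.9% at n = 57 and 90.8% at n = 200. No particular n is required to meet it. The second row shows that the criterion does not separate 80% from 70% at this size.

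**4. Precision that 57 patients do give.** The 95% half-width by normal approximation is 1.96 × √(0.21/57) = 11.9 points at 70% and 1.96 × √(0.16/57) = 10.4 points at 80%. The 90% half-width at 70% is 10.0 points.

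**The case against.** The strongest objection is that section 6.2 never says the interval must exclude 70%. It reports 70% as an observed rate and asks only that 80% be included. On that criterion a true 80% would fall outside the interval in only about 3-12% of trials, so roughly 90% is attained. A single-arm phase II trial may also reasonably be sized for precision.

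Much of this stands. A reader might infer that the trial simply has 39% power and would miss a true 80% six times in ten. The protocol does not support that without a condition, because it contains no rule based on rejecting 70%. The 39% belongs to a test against 70% at the level in section 6.1. That test is a natural reading, given the stated aim of finding 80% and the only reference rate in the section, but it is still a reading. A reader might also infer that the 90% is a confidence level mislabelled as power. The match with 56.8 makes this likely, but it is an inference. Any conflict between a 90% interval and the 5% level in section 6.1 depends on it.

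The objection does not rescue the sentence. Coverage of about 90% follows from choosing a confidence level near 90%, not from enrolling 57 patients, so the claim that this criterion requires 57 is wrong on the literal reading too. Nor can it be left to an analysis plan, because the protocol itself states the number and its justification.

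**Conclusion.** Section 6.2 is wrong as written. Read as a test of 70% at two-sided 5%, exact power at a true 80% is about 39%, not 90%, and 90% power would need about 200 patients. Read literally, the 90% is interval coverage, nearly independent of sample size, and the criterion would also be met in about 44-66% of trials with a true rate of 70%.

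These figures assume a binary endpoint known for all 57 patients and a fixed reference of 70%. Allowing for sampling error in the 300 historical patients lowers power further, to about 32%. The 44-66% range reflects the unstated confidence level and interval method. The origin of 57 as a 90% interval of ±10 points is probable, not documented.

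The finding does not show that 57 patients are too few for a precision-based phase II estimate. It shows that the stated justification does not support the number and would mislead anyone relying on the 90%.

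**What to change.** Keep 57 patients and reword section 6.2:

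- Delete the reference to 90% power and the statement that this criterion requires 57 patients.
- State that the size is precision-based. With 57 patients the 95% confidence interval has a half-width of about ±12 points at an observed 70% and about ±10 points at 80%.
- State that a two-sided 5% exact test against 70% rejects at 47 or more of 57, with about 39% power at a true 80% and 90% power only at a true rate of about 87%.
- State that inclusion of 80% in the interval is not by itself evidence of improvement over 70%.

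If 90% power against 70% at a true 80% is what was intended, the alternative is to define that test and resize to about 200.

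The recommended change costs wording only. It needs no extra patients and no change in conduct. Its downside is that the stated power becomes much less favourable.
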